7.2 Permitted Medications/Treatments

- Eye-masks may be used 24/7 when phototherapy is being used in the first weeks of life.
- The use of eye-masks can be permanently or temporarily discontinued if a skin, eye or ear condition develops that precludes their use. All other interventions will be continued where practically possible to ensure the active intervention participant is still subjected to a cycled environment.
- Ear-plugs may be applied 24/7 for infants during high-frequency ventilation if this practice is in accordance with normal nursery protocols (normally short-term).
- Respiratory stimulants (e.g. caffeine) will be regulated to 8 am dosing for all infants, when prescribed, to avoid pharmacologic confounding on circadian rhythm development.
- If postnatal glucocorticoids are prescribed for severe lung disease, they will be given at 6 am/6 pm to reduce disruption to nocturnal sleep.

7.3 Monitoring of Participant Compliance

Noise levels will be documented for 24 hour periods on days 7, 14, 28 and 56, and at 36 w PMA at participating primary sites (see Figure 2 – Detailed Neonatal Data Collection). These records and appropriate placement of the intervention devices will be audited frequently by the trial site co-ordinator, and intermittently by the co-ordinating trial team.

8 The CIRCA DIEM Biobank (relevant to West Australian study participants and study sites)

Samples collected from Western Australian participants in the CIRCA DIEM Study who consent to participate in the Infection and Immunology sub-study will form the basis of the CIRCA DIEM biobank ("The Biobank"). The purpose of this biobank is to explore biological mechanisms that may contribute to neonatal outcomes of infants born prematurely as well as their well-being throughout childhood, adolescence and into adulthood. We anticipate that additional samples will be added to the CIRCA DIEM Biobank in subsequent years as follow-up studies of the CIRCA DIEM cohort are established. Samples may include saliva, buccal cells, nasal viral and epithelial swabs, epithelial cells, faeces, and blood. Whereas initial collection of the samples from CIRCA DIEM participants will require parental consent to sample collection and storage, CIRCA DIEM participants will be asked for consent for the Biobank to continue to retain their samples once they achieve their majority (18 years).

The Biobank custodian will be Telethon Kids Institute, and the Biobank will be managed on the Institute's behalf by a CIRCA DIEM Biobank Governance Committee chaired by [name], as the Principal Co-ordinating Investigator of the CIRCA DIEM study and two additional Biobank committee members with expertise in biobanking governance and management. The Founding Members of this committee will include [name] and [name] in addition to [name].

Biobank data will be managed within OpenSpecimen software, hosted on a secure server at Telethon Kids Institute and in accordance with relevant legislative requirements. Samples obtained and stored in the biobank will be labelled with a study number in addition to important information relating to the specific sample including date and time of sampling, as well as nature of the sample. Labelling will not include any identifiable information, but will be potentially reidentifiable as custodians of the biobank will retain a register linking study numbers to identifiable information. Parents (and participants when able to give informed consent) will be invited to give their permission for their infant/child's samples to be retained in the CIRCA DIEM biobank for future research studies relevant to understanding how prematurity impacts later wellbeing and/or susceptibility to illness.

Researchers wanting to access the Biobank will need to submit an application to the CIRCA DIEM Biobank Governance Committee and obtain ethical approval for their proposed study. Researchers will only be able to access de-identified data from the CIRCA DIEM study, and will be required to ensure the safety and security of data provided in accordance with Good Clinical Practice (GCP). The key to the code that permits reidentification of these samples will remain with the CIRCA DIEM Governance Committee.

9 Assessment of Safety

9.1 Risks and Benefits

9.1.1 Risks

This study is a low-risk research project. The eye-mask and ear-plugs are worn routinely by infants during periods of phototherapy and high-frequency ventilation respectively. The silicone ear-plugs are soft and mouldable to the ear canal. Routine cycled use of any of the interventional devices will not be a standard of care in any of the recruiting units. The placement of the eye-mask band over the ear acts as a safety measure against accidental dislodgement of the ear plug.

The circadian rhythm biological sub-study includes use of buccal and saliva swabs. These swab procedures involve negligible discomfort. There is a risk of aspiration/choking if the swabs are not used as directed i.e. was not held securely by the investigator/caregiver. Swabbing will be co-ordinated with feeds (obtained immediately pre-feed) to minimise impact on wakefulness on sampling days. The positioning of the actimeter on the ankle of the infant and wrist of the primary caregiver is anticipated to have negligible discomfort. The use of this wearable device on the infant participants is minimised through nurse checks every 3 to 4 hours while they are staying in hospital, the use of a neonatal posey (small strap designed specifically for pre-term infants), limited exposure (24 hours) and is limited to babies >1kg.

There is a risk that assessments of the mental well-being of primary caregivers may identify clinical conditions requiring medical assessment and care. All mental well-being questionnaires will be reviewed and graded promptly by the psychological assessment team to ensure prompt referral to medical care for individuals considered to be at risk.

9.1.2 Benefits

The potential benefits for infants assigned to the intervention include earlier development of circadian rhythm resulting in improved feed tolerance, growth, reduced illness severity, earlier discharge and improved long-term neurodevelopmental outcomes.

The potential benefits for the parents of infants assigned to the intervention include improved post-discharge sleep cycling, enhanced parent-infant attachment and improved mental well-being.

9.2 Safety

9.2.1 Data and Safety Monitoring Committee (DSMC)

The DSMC will review the study data at 25 %, 50 %, 75 % recruitment to assess the safety of the intervention and to adapt the sample size as trial data accumulate. The DSMC may stop the trial if there are concerns that the study intervention is harmful to the patient, as defined prospectively in the charter. Key safety outcomes will be assessed at 36 w PMA and will include:

A study-related adverse event (AE) will be:

- 1. Necrotising enterocolitis Stage IIb or greater (Bell's Criteria)
- 2. Retinopathy of prematurity with a Stage III or greater
- 3. Skin damage from use of wearables
- 4. Any perceived safety issue associated with the intervention devices

A study-related serious adverse event (SAE) will be:

- 1. Death before discharge home from hospital deemed potentially associated with the intervention.
- 2. Death after discharge and before 2 years of age associated with the intervention.
- 3. Any perceived life-threatening event during hospitalisation associated with the intervention devices.

9.2.2 Adverse event reporting

All adverse events will be documented in REDCap prospectively and reported to the respective Ethics Committee and the DSMC. The Telethon Kid's Institute will be responsible for providing the Annual Safety Report to the HREC.

9.2.3 Follow-up of adverse events

Type and duration of follow up following any adverse event will be subject to the discretion of the treating physician.

10 Data Management, Statistical Analysis and Record Keeping

10.1 Statistics and Interim Analysis

Data will be analysed in R software (open-source) on an intention to treat basis by the trial biostatistician ([name]) and performed blinded to study group assignment.

Missing data will be handled via multiple imputation.

Children unable to be tested on Bayley-4 due to death, disability, severe delay or performance below threshold for individual composite scores will be assigned a score of 49.

Comparability of study groups at baseline will be based on patient demographic data (birth weight Z-score, gestation, exposure to chorioamnionitis and maternal steroids, maternal shift work) and baseline physiological circadian rhythmicity determined at randomisation.

Descriptive statistics will include mean (SD), median (IQR) for continuous variables with symmetric and asymmetric distributions, respectively, and counts/percentages for categorical variables.

Cognitive scores between the two groups at 2 years cPNA (primary outcome) will be analysed using (1°) ttest and (2°) linear mixed effects regression, adjusted for socioeconomic status, parental risk index, sex, birthweight Z score, gestation age, antenatal and postnatal steroid use, key neonatal morbidity count and including random effects for multiple birth ID and site. The false discovery rate employed for all secondary analyses will use the Benjamini-Hochberg algorithm.

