5.3 Minimisation of Bias

Infants meeting study eligibility criteria will be randomised to a control environment or a cycled environment (light and noise) from birth until discharge. Randomisation will use variable block sizes (block size 4 to 6) stratified by both gestation (<28 w, 28⁰-31⁶ w PMA) and study site, using the concealed randomisation facility built into the REDCap database via computer generated, randomisation tables developed and uploaded by the trial biostatistician ([name]) and maintained by the Trial Management Team at the Telethon Kids Institute. Randomisation will maintain equal group sizes between the two study arms. Infants from multiple pregnancies will be assigned to the same group, to ensure planned secondary analyses on parent mental well-being and attachment are not confounded by conflicting infant circadian rhythms.

Blinding of families, healthcare providers during initial hospitalisation, and the co-ordinating study investigators to group allocation is not possible for this intervention. However, outcome assessors and data analysts will be blinded to allocation.

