The primary sites currently include the King Edward Memorial Hospital (WA), Fiona Stanley Hospital (WA), Monash Newborn at Monash Children's Hospital (VIC), Women and Children's Hospital (SA), Royal Prince Alfred Hospital (NSW), Westmead Hospital (NSW), Gold Coast University Hospital (QLD), Joan Kirner Women's and Children's Hospital (VIC), Nepean Hospital (NSW), Wellington Hospital (New Zealand), Auckland City Hospital (New Zealand), Southmead Hospital (Bristol, UK), University College London Hospitals (UK) and British Columbia Children's and Women's Hospitals (Vancouver, Canada).

A sample size of 954 is required to detect a difference of at least 4 points on the cognitive sub-score at 2 years corrected postnatal age. This calculated sample size assumes 90 % power, 5 % significance level, standard deviation of 15 points, with a 2-sided t-test, 10 % loss to follow-up, and 30 % adjustment for multiple births. A blinded interim analysis will be performed after 50 % of participants have reached the 2 year endpoint to assess the assumptions in the sample size calculation.

The circadian biology/physiology sub-study (n=48/strata) has an 80 % power to detect a significant difference (at the 5 % level) in trend for the melatonin amplitude between control and intervention groups, using Wilks likelihood ratio test, assuming: 6 observations for each individual at time points 0, 1, 2, 4, 8, 12 weeks; an exponential increase in control means from 0 to 50 pg/mL and intervention means from 0 to 100 pg/mL; a standard deviation of 23.6 pg/mL;⁵⁸ a LEAR model for monotonically decreasing correlation between individual observations with a base correlation of 0.5 and a decay rate of 0.3, and; the open-source, web-based GLIMMPSE.57

Recruitment rates will be determined by the 477 infants required for the < 28 w gestation strata, who are most in demand for enrolment in neonatal clinical trials. Recruitment of an average of 18 infants/month in the < 28 w strata is achievable across 9-10 neonatal units (average 2 infants/month/site) to achieve our full study enrolment by 30 months after obtaining full study funding. The participation of up to an additional 10 study sites will be sought as necessary to ensure full study recruitment targets are achieved.

6.2 **Participant Inclusion Criteria**

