10.2 Sample Size, Study Power, and Significance

A sample size of 954 is required to detect a difference of at least 4 points on the cognitive sub-score at 2 years corrected postnatal age.

This calculated sample size assumes 90 % power, 5 % significance level to detect a mean difference of 4 points in the primary outcome for a known population standard deviation of 15 points, with a 2-sided t-test, 10 % loss to follow-up, and 30 % adjustment for multiple births.

- A 2 sample t-test for mean difference of 4 points with SD of 15 points = 297 subjects/group resulting in a total unadjusted sample size of 594.
- The unadjusted sample size was rounded up to 600, then adjusted for expected 30 % prevalence of multiple births in the recruited population, and a 10 % loss to follow-up for the long-term outcome. 600/0.7/0.9 = 952.3 subjects
- The final sample size was rounded to 954, to ensure an even allocation of subjects to the two study groups.

A blinded interim analysis will be performed after 25 % and 50 % of participants have reached the 2 year endpoint to assess the assumptions in the sample size calculation.

Sample sizes for sub-studies target 80 % power to detect 0.5 SD mean difference with significance at the 5 % level.

Circadian rhythmicity will be assessed using cosinor analysis (non-linear regression) to determine mesor, amplitude, and acrophase of rhythms.

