10.4 Selection of Participants for Analyses

All infants recruited in the study will be evaluated statistically provided the participant is not withdrawn from the study before discharge from the hospital, and parents are satisfied for us to use the data.

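### The 1° analysis of the primary outcome is an ordinary t-test, whose standard error does not match a design that co-randomises multiples and stratifies by gestation and site

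*Protocol*

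**What the plan says.** - **Analysis.** Section 10.1 says the primary outcome "will be analysed using (1°) ttest and (2°) linear mixed effects regression". The terms that reflect the design, "including random effects for multiple birth ID and site", belong to the 2° model only. That model also adjusts for, among other things, gestational age, postnatal steroid use and a count of key neonatal morbidities.
- **Allocation.** Section 5.3 says "Infants from multiple pregnancies will be assigned to the same group", so the sibling set is the unit of randomisation. It also says "Randomisation will use variable block sizes (block size 4 to 6) stratified by both gestation" and by study site.
- **Who is analysed.** Section 10.4 says "All infants recruited in the study will be evaluated statistically provided the participant is not withdrawn" before discharge. There is no rule taking one infant per set.
- **Sample size.** Section 10.2 rests on the same test: "A 2 sample t-test for mean difference of 4 points with SD of 15 points = 297 subjects/group". The total is rounded to 600, then "adjusted for expected 30 % prevalence of multiple births in the recruited population" and for 10% loss to follow-up.

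**The concern.** An ordinary two-sample t-test estimates the variance of the difference as if each infant had been allocated separately and without restriction. Neither is true here.

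Siblings share an arm and tend to have similar scores, so the arm means vary more than the t-test assumes and its standard error is too small. Stratified blocks balance gestation and site between arms, so any score variance due to those factors largely drops out of the true variance of the difference. The t-test leaves that variance in its error term, so its standard error is too large.

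The protocol recognises the clustering twice, in the 2° random effect and in the sample-size inflation, but not in the test that decides the trial. At stake is whether the headline p-value has its stated 5% level and whether the 95% interval covers 95%. A borderline t-test result that disagreed with the mixed model would leave the conclusion open to challenge.

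**Working it through.** **1. The plan's own figures.** For a difference of 4, SD 15, two-sided 5% and 90% power, the exact t calculation gives 297 per arm (power 0.9005). Then 600/0.7/0.9 = 952.4, which the plan rounds to 954. Both reproduce.

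**2. Inputs.** From the protocol: 1:1 allocation, siblings together, 30% multiples, two gestation strata, and the 14 primary sites listed in Section 6.1 (28 strata). Assumed, because the protocol gives neither:
- total sibling correlation of the score, ρ = 0.3 to 0.8;
- share of score variance explained by the strata, R² = 0, 0.10 or 0.20.

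The 30% is read as the share f of infants who are multiples, and all multiples are taken as twins.

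**3. Formula.** Siblings share site and, in practice, gestation stratum, so the stratum part of the variance is already inside ρ and must not be counted twice. The ratio of the true variance of the difference to the t-test's variance is

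V = (1 − R²) + f(ρ − R²), with f = 0.30,

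and the true two-sided error of the nominal 5% test is 2[1 − Φ(1.96/√V)].

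**4. Results.**

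| R² | ρ | V | True error |
|---|---|---|---|
| 0 | 0.3 | 1 + 0.3×0.3 = 1.09 | 0.0605 |
| 0 | 0.8 | 1 + 0.3×0.8 = 1.24 | 0.0784 |
| 0.10 | 0.3 | 0.90 + 0.3×0.2 = 0.96 | 0.0455 |
| 0.10 | 0.8 | 0.90 + 0.3×0.7 = 1.11 | 0.0628 |
| 0.20 | 0.3 | 0.80 + 0.3×0.1 = 0.83 | 0.0314 |
| 0.20 | 0.8 | 0.80 + 0.3×0.6 = 0.98 | 0.0477 |

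With R² = 0 the correct standard error is √1.09 = 1.044 to √1.24 = 1.114 times the t-test's, and the nominal 95% interval covers about 94% to 92%. The two faults cancel exactly where V = 1, that is R² = 0.3ρ/1.3: 0.07 at ρ = 0.3 and 0.18 at ρ = 0.8.

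**5. Simulation.** The set-up was 858 infants, 30% twins allocated together, 28 strata, permuted blocks of 4 or 6, and 3,000 runs per setting. Rejection rates under no effect were 0.049 (ρ = 0, R² = 0), 0.067 (ρ = 0.5, R² = 0), 0.079 (ρ = 0.7, R² = 0), 0.053 (ρ = 0.5, R² = 0.10) and 0.062 (ρ = 0.7, R² = 0.10). The formula gives 0.050, 0.068, 0.075, 0.052 and 0.059, which agree within simulation error.

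**6. Power.** With 954 × 0.9 = 858.6 infants analysed and a design effect of 1 + 0.3ρ, a cluster-aware analysis has power 0.963 at ρ = 0.3 and 0.939 at ρ = 0.8, taking no credit for the strata. The inflation of 1/0.7 = 1.43 exceeds the twin design effect even at ρ = 1 (1.30).

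**7. Sensitivity to the 30%.** If 30% is instead the share of pregnancies, all twins, then f = 0.6/1.3 = 0.46. With R² = 0 the error becomes 6.6% to 9.4% for ρ = 0.3 to 0.8. Power at ρ = 0.8 is still 0.916.

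**The case against.** **The direction is not known.** A reader might infer that the t-test is anti-conservative and that the trial's error rate is clearly above 5%. The protocol does not support this. It gives neither the sibling correlation nor the stratum variance, and the faults pull in opposite directions. Stratifying by gestation and site, and modelling both in the 2° analysis, suggests the investigators expect them to matter. Section 10.1 also assigns a score of 49 for death or severe disability, and if those outcomes concentrate below 28 weeks, stratum variance rises. This objection stands, and the case with no stratum variance is only one end of the range. It does not rescue the t-test, because a confirmatory 5% level should not rest on two unknown quantities happening to cancel. Where the test is conservative, it discards precision that the stratification was meant to provide.

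**A clustered analysis is already planned.** This is true, so the question is which analysis decides, not whether a method is missing. A reader might then conclude that exchanging the two analyses is enough. It is not: the 2° model adjusts for postnatal steroid use and neonatal morbidity count, both arising after randomisation and possibly affected by the intervention.

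**The sample size allows for multiples.** It does, and power is secure. A larger N does not change how the t-test computes its standard error.

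**The SAP may settle it.** An SAP is not at hand, but the protocol does not leave the test open. It names the t-test as 1° and builds the sample size on it. Section 10.3 sends deviations from the statistical plan to updated versions of the protocol, so Section 10.1 is the place to correct this. The reading of 1° and 2° as primary and secondary is the natural one, though the protocol does not define the symbols.

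**Conclusion.** The mismatch is established from the text: the deciding test assumes independent, unstratified infants in a design that has neither property. Its size is moderate and its sign is open. With 30% of infants as twins and a total sibling correlation of 0.3 to 0.8, the true error of the nominal 5% test runs from about 3.1% (strata explain 20%, correlation 0.3) to about 7.8% (strata explain nothing, correlation 0.8). With 10% explained by strata it is about 4.5% to 6.3%. All of these rest on the assumed correlation and stratum variance. A claim that the type I error is definitely inflated, or that the trial is underpowered, would go beyond the documents.

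**What to change.** In Section 10.1, replace the plain t-test as the primary analysis with a linear mixed model or GEE for the cognitive score that contains treatment arm, gestation stratum and site, is clustered on multiple-birth set, and includes pre-randomisation covariates only. Do not carry over postnatal steroid use or the neonatal morbidity count from the present 2° model. Keep the unadjusted mean difference as a supportive analysis with a standard error robust to clustering on the multiple-birth set.

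Keeping the unadjusted difference as primary with that robust standard error would be a smaller repair. It would deal with the siblings but not recover the precision from stratification.

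The cost is a small re-specification of the model, made before unblinding. Arm, gestation, site and multiple-birth ID are already recorded or already in the planned analyses, so no new data and no additional infants are needed.

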4.3 Secondary Hypotheses and Outcomes

Exposure to cycled light and noise from birth until discharge home will: 1) improve neurodevelopmental sub-scores and neurobehaviour at 2 years cPNA; 2) not increase mortality or neonatal morbidities; 3) result in more rapid development of endogenous circadian rhythms; 4) reduce parental depression and anxiety and improve parent-infant interactions; and 5) decrease socio-economic costs of premature birth.

5 Trial Design

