5.1 Study Endpoints

- 5.1.1 Primary outcome
 - Cognitive scores on the Bayley-4 around 2 years cPNA⁴⁶

The Bayley-4 is an individually administered instrument to assess developmental functioning in infants and young children from the age of 1 month to 42 months of age. The Bayley-4 is the current, universal national test of early development. The Bayley-4 sub-scores include cognitive, language (composite of receptive and expressive communication) and motor (composite of fine motor and gross motor). Scores are adjusted for prematurity, with a distribution centred on 100 with a standard deviation of 15. A 4-point change in cognitive score provides similar cognitive advantage as breast-feeding for at least 8 months and may be sufficient to obtain semi-skilled rather than unskilled work.⁴⁷ Expertise in Bayley-4 test administration is available within all Australian neonatal centres. A copy of the child's Bayley-4 results can be provided to parents upon request.

The trial will aim to conduct Bayley-4 assessments at 2 years cPNA. If participants are unable to undertake their Bayley-4 assessment at 2 years cPNA, a later Bayley-4 assessment will be undertaken as soon as reasonably possible and up to a maximum participant age of 3 years cPNA.

5.1.2 Secondary outcomes

Comprise short-term and longer-term neurodevelopmental and clinical outcomes as well as targeting physiological and molecular indicators of circadian rhythm development to inform mechanism and effectiveness of the intervention.

5.1.2.1 *Short term secondary outcomes*

- Survival to 36 w postmenstrual age (PMA)
- Weight, length, head circumference, and growth velocity (36 w PMA; 2 m, 6 m, 12 m cPNA)
 - Duration of hospitalisation
 - Tertiary hospital
 - Total duration of hospitalisation prior to first discharge home
- Severity of respiratory disease

•

- BPD (defined by the NICHD and shift of the oxyhaemoglobin dissociation curve),
- right shift of the SpO₂/P₁O₂ curve at 36 w PMA relative to the fetal oxyhaemoglobin dissociation curve
- duration of mechanical ventilation,
- duration any respiratory support
- days of oxygen supplementation
- Other neonatal morbidities including:
 - NEC stage II or more on Bell's classification
 - ROP stage II or stage III ROP, and presence of 'plus' disease or greater on ICROP3
 - Brain Grade 3 or 4 IVH, and presence of PVL
 - Sepsis defined as number of confirmed (blood culture positive) episodes of sepsis

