5.1.2.2 Long-term (2 y cPNA) secondary outcomes

- Survival
- Proportion of scores < 1 SD and < 2 SD below mean, for the primary cognitive sub-score outcome at 2 y cPNA
- Individual components of the Bayley-4 at approximately 2 y cPNA
- Neurobehaviour using the Infant Toddler Social-Emotional Assessment (ITSEA)⁵³
- Social communication using the Communication and Symbolic Behaviour Scales Infant-Toddler Checklist (CSBS-ITC) for early recognition of risk behaviours that may be predictive of later behavioural difficulties such as diagnosis of autism spectrum disorder
- Growth velocity
- Anthropometry including weight, height, BMI, fat-free mass
- Primary caregiver mental well-being
 - GAD-7
 - Center for Epidemiologic Studies Depression Scale Revised (CESD-R).
- 5.1.3 Circadian rhythm biological sub-study (KEMH only, n=~70): confirming intervention effect on rhythms
 - Time to onset, mesor, amplitude, and acrophase of circadian rhythms in temperature, heart rate, oxygen saturation, salivary melatonin and cortisol and/or urinary melatonin, and buccal cell clock gene expression at study entry, 7 d, 14 d, 28 d and then 4 weekly until discharge home.
- 5.1.4 Social Communication sub-study (n=infants identified at risk of ASD using the CSBS-ITC, in centres where ADOS-2 testing is available)
 - Assessment at 2 years corrected postnatal age with The Toddler Module of the Autism Diagnostic Observation Schedule - Second Edition (ADOS-2)⁵⁴. Two outcomes will be reported from the ADOS-2.
 - the continuous scores of the ADOS-2 (i.e., autism behavioural severity)
 - the dichotomous outcome of whether or not children exceed the 'ASD' threshold (to be defined).
- 5.1.5 Neonatal lung function and body composition sub-study (KEMH only, n=128)
 - Tidal volume
 - Respiratory rate
 - Area under the flow volume curve
 - Body volume
 - Body fat and fat free mass, and % body fat

5.1.6 Measurement of infant sleep quality and duration sub-study

- Parents will be asked to complete the Brief Infant Sleep Questionnaire (BISQ-R; 33 items) at 2 months and 6 months corrected postnatal age, to provide detail on their infants sleep behaviours over the previous 2 weeks.
- Parents will also be asked to keep a sleep diary of their own sleep behaviours over the same interval.

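### The Benjamini-Hochberg correction covers all secondary analyses, including mortality and neonatal morbidity, so it can only keep or lower the chance of flagging a real increase in harm

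*Protocol*

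**What the plan says.** Section 10.1 of the protocol sets the multiplicity rule in one sentence: "The false discovery rate employed for all secondary analyses will use the Benjamini-Hochberg algorithm". It makes no exception for safety outcomes. The error rate to be controlled and the grouping of tests into families are not given.

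Section 5.1.2.1 lists survival to 36 weeks, BPD and a group headed "Other neonatal morbidities including" (NEC, ROP, IVH/PVL, sepsis) as short-term secondary outcomes. They stand beside growth, length of stay and questionnaire scores. Section 5.1.2.2 lists survival again at 2 years, beside the Bayley-4 components and behaviour scales.

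Section 4.3 makes it a secondary hypothesis that the intervention will "not increase mortality or neonatal morbidities". No margin or confidence-interval criterion goes with it.

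Safety also has a separate route. Under sections 5.7 and 9.2.1 the data safety monitoring committee (DSMC) reviews data at 25, 50 and 75 % recruitment, and "The DSMC may stop the trial if there are concerns that the study intervention is harmful to the patient, as defined prospectively in the charter". No multiplicity correction is attached to that review.

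**The concern.** False-discovery control guards against declaring differences that are not there. For efficacy outcomes that is the cautious direction. For a hypothesis that harm is not increased, the costly error is the opposite one: missing a real increase. A Benjamini-Hochberg adjusted p-value is never smaller than the raw one, so placing death and morbidity under the rule cannot help to detect harm and will usually hinder it. Adding efficacy outcomes without real effects to the same family raises the bar further.

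At stake is how the final report describes a true rise in mortality or a major morbidity. A difference whose unadjusted 95 % interval excludes zero could be labelled non-significant after correction. This does not turn on a detail left to the statistical analysis plan, because the protocol itself fixes the scope of the correction.

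**Working it through.** **1. The plan's own figure.** Section 10.2: "This calculated sample size assumes 90 % power, 5 % significance level", and "A 2 sample t-test for mean difference of 4 points with SD of 15 points = 297 subjects/group". The normal approximation gives 2 × (1.960 + 1.282)² × 15² / 4² = 295.5, so 296 per group. The t-test version gives 296.5, so 297. Then 600 / 0.7 / 0.9 = 952.4, rounded up to 954. The figure reproduces. With equal allocation (section 5.3) this is 477 per arm. No event rate or power is given for mortality or morbidity.

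**2. Assumptions.** Two-sided tests; false discovery rate 0.05; all 477 infants per arm counted; independent tests; no allowance for clustering of multiples. Control rates are 5–10 %. The family has 10 to 62 tests. Counting each time point in sections 5.1.2.1 and 5.1.2.2 separately gives about 62 (48 short-term, 14 long-term), and collapsing time points gives about 30.

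**3. One case by hand: 5 % v 10 %.** SE = √(0.05×0.95/477 + 0.10×0.90/477) = 0.01698, so the standardised difference is 0.05 / 0.01698 = 2.945.
- Unadjusted, α = 0.05, critical value 1.960: power = Φ(2.945 − 1.960) = Φ(0.985) ≈ 84 %.
- Family of 20, nothing else rejected, α = 0.05/20 = 0.0025, critical value 3.023: power = Φ(2.945 − 3.023) = Φ(−0.078) ≈ 47 % (about 46 % with a pooled variance).

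**4. Allowing for adaptivity.** The Benjamini-Hochberg threshold is 0.05 × k/m, where k is the number of rejections and m the number of tests, so it relaxes as other outcomes are rejected. The procedure was simulated with 40,000 runs per setting. Either no other outcome had a real effect, or about half did, each with 80 % power. Power to flag harm:

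| Event rates | Unadjusted | m = 20, none | m = 20, half | m = 40, none | m = 40, half | m = 62, none | m = 62, half |
|---|---|---|---|---|---|---|---|
| 5 % v 10 % | 84 % | 48 % | 74 % | 40 % | 72 % | 35 % | 71 % |
| 8 % v 14 % | 85 % | 49 % | 74 % | 41 % | 73 % | 36 % | 73 % |
| 10 % v 15 % | 65 % | 26 % | 50 % | 19 % | 49 % | 17 % | 48 % |
| 6 % v 12 % | 90 % | 61 % | 82 % | 52 % | 82 % | 47 % | 81 % |

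With m = 10 and no other effects, the first three rows give about 56 %, 58 % and 33 %. The smallest loss in these settings is about 8 points (6 % v 12 %, m = 20, half). The largest is about 49 points (5 % v 10 %, m = 62, none).

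**5. What the trial can say without adjustment.** The 95 % half-width for a risk difference is 1.96 × √(2p(1−p)/477). This is 2.8 points at p = 5 %, 3.4 at 8 % and 3.8 at 10 %. Even an unadjusted non-significant test is therefore compatible with an increase of several points.

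**The case against.** The strongest reply is that the rule affects labels in the final secondary analysis and not the trial's protection of infants. The DSMC reviews safety three times against a charter definition of harm, and section 9.2.2 sends adverse events to it and to the ethics committees, all without correction. Deaths also enter the primary outcome as a score of 49. This stands as far as it goes. But the DSMC review covers safety while the trial runs and does not govern the final between-arm comparison that bears on hypothesis 2. The score of 49 dilutes mortality within a cognitive mean.

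Second, Benjamini-Hochberg adapts. If many outcomes move, or if harms occur together, the bar eases, and the worst-case threshold of 0.05/m overstates the loss. That also stands, and is why the size is given as a range.

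Third, low event rates already limit power. For 6 % v 9 %, unadjusted power is only 42 %, so a non-significant result is the likelier one even without correction. True, but with 62 tests the figure drops to about 13 % at the fifth-ranked threshold (0.05 × 5/62).

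Fourth, adjusting p-values does not prevent unadjusted intervals from being reported. Correct, but section 10.1 does not call for them.

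A reader might infer more: that the correction was chosen to blunt detection of harm, that a single family of all secondary tests is prescribed, or that an adjusted null result will be taken to confirm hypothesis 2. The document supports none of these. It gives no reason for the choice, does not define families, and states no decision rule for hypothesis 2.

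**Conclusion.** The point holds in a limited form. A stated rule, read as written, puts mortality and neonatal morbidity under a false-discovery correction. For a hypothesis of no increase, that works in the non-conservative direction. Under the assumptions listed, the loss of power to flag harm is roughly 10 to 50 percentage points, smallest when many other outcomes have real effects and largest when none do. The event rates, the false discovery rate, the number of tests and their independence are all assumptions, so the range illustrates the size and does not predict it. Reading a non-significant result as reassurance is a foreseeable risk and not a stated plan. Lifting the correction would not by itself settle hypothesis 2, because the protocol gives no margin or interval criterion for it. The change is worth making before the final analysis, but it does not threaten the primary result or the interim safety oversight.

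**What to change.** Amend section 10.1 in three respects:
- Limit the Benjamini-Hochberg family to secondary efficacy outcomes.
- Report mortality and the neonatal morbidities as safety outcomes, each with an unadjusted between-arm difference and 95 % confidence interval.
- State that a non-significant p-value will not be taken as showing no increase. The conclusion on hypothesis 2 would instead be worded as the largest increase that the upper confidence limit does not exclude.

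A formal claim of no increase would need a margin stated in advance, and an upper limit without one describes but does not decide. For orientation, with equal true rates of 5 %, one-sided 0.025 and 90 % power, a 5-point margin needs 400 per arm and a 4-point margin 624. At 8 %, a 5-point margin needs 619. The planned 477 per arm would therefore support such a claim in only some settings.

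The cost is a sentence or two of protocol text and a slightly higher chance of a false harm signal, which is the usual trade for safety outcomes. The descriptive wording needs no extra infants or data.
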